## 1.4 Dose Rationale and Risk/Benefits

Only one Foley catheter is placed during a patient's labor induction course. The single balloon can be filled with 30-80 mL of normal saline. Our equipment best facilitates 30-60 mL. A study by Delaney et al. demonstrated that inflation with 60 mL increased the likelihood of delivery within 12 hours compared to 30 mL without any adverse maternal or neonatal outcomes [13]. Therefore, 60 mL was elected for this study.

Common adverse effects of transcervical Foley catheters include discomfort and vaginal spotting. The patient may feel uncomfortable during placement of the Foley catheter and while the Foley catheter is in place. Similarly, women in the inpatient group can expect discomfort during the initiation of their labor induction as well, whether with the Foley catheter or vaginal misoprostol. Pain control options as described elsewhere in this document will be available for patient comfort. Available data suggests that the Foley catheter is tolerable from a pain perspective. Pennell and colleagues evaluated pain associated with the Foley catheter and found that pain with insertion was rated as 4/10 and pain during cervical ripening was 2/10 [14]. Overall satisfaction with induction of labor for Foley catheter was 8/10, which was equivalent to the other cervical ripening agents studied.

Patients may also commonly experience vaginal spotting after placement of a Foley catheter. This is typically from cervical manipulation rather than clinically significant placental abruption. In the majority of cases, these etiologies can be distinguished by experienced clinical evaluations. If there is suspicion that vaginal bleeding represents placental abruption, the patient will be excluded from the trial and kept in the inpatient setting until delivery. The amount of blood lost from vaginal spotting is not clinically significant and is common during induction of labor in the inpatient setting.

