Less likely risks include the following: artificial or spontaneous rupture of membranes, initiation of spontaneous labor, and placental abruption, both clinically significant and insignificant. The patient will be educated regarding these risks. Should any of these events be diagnosed while the patient is in the Family Birth Center for post Foley monitoring, she will be kept as an inpatient until delivery and excluded from the trial. Should any of these occur at home, the patient will return immediately to the Family Birth Center as outlined in both verbal and written instructions.

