**IV. Protocol for the intervention group (Both Randomized Control Trial and Prospective Study)**

- A. The patient will present to the Family Birth Center at 0730 or 1930.
- B. A nonstress test (NST) will be performed
  - 1. The fetal heart rate (FHR) is observed by external monitoring for at least 20 minutes. The FHR is observed for the presence of accelerations, at least 2 in 40 minutes that peak at least 15 beats per minute above the baseline and last for at least 15 seconds. The absence of at least 2 accelerations in up to 40 minutes is considered nonreactive.
  - 2. A nonreactive NST, the presence of  $\geq 3$  variable decelerations in a 20 minute period, late-appearing decelerations, or any deceleration lasting  $\geq 1$  minute should be considered criteria for exclusion.
- C. An ultrasound will be performed for fetal presentation and amniotic fluid index.
- D. A cervical exam will be performed with calculation of a Bishop score.
- E. The patient will be asked the following standard questions.
  - 1. Are you experiencing any of the following: regular, painful contractions? Decreased fetal movement? Vaginal bleeding? Leakage of fluid from the vagina concerning for rupture of membranes? Fevers or chills?
  - 2. She will be excluded from the trial based on her answers, as described in section 4.2 "Exclusion Criteria."
- F. A Foley catheter will be placed if the following criteria have been met: the nonstress test is reactive, the fetal presentation is cephalic, the amniotic fluid index is 5 centimeters or more, the Bishop score is  $<9$ , the cervical dilation is  $<3$  cm, and she has no other clinical characteristics that exclude her from the trial.
- G. An obstetric provider will place a 16 French Foley catheter through the internal os. The balloon will be inflated with 60cc of normal saline. The distal end of the Foley will be taped to the patient's inner thigh.
- H. The fetal heart rate tracing will be monitored for 1 hour after Foley placement.
- I. The patient will be sent home if the following criteria are met: the fetal heart rate tracing is reactive and category I; there is no evidence of rupture of membranes, spontaneous labor, or vaginal bleeding more than spotting; and maternal vital signs are within normal range.
- J. Pain control options

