### 3.4 Primary Safety Endpoints

The primary safety outcomes are as follows: heavy vaginal bleeding, severe pain (return to hospital overnight for unrelieved pain), mode of delivery, intrapartum complications (as described above), and fetal outcomes (as described above). These will include overall fetal and maternal survival rates. Based on previous studies, we do not anticipate any difference between safety endpoints in the inpatient vs. outpatient groups.

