Finally, the pregnant woman may become excluded from study shortly after arrival to the Family Birth Center for initiation of the planned induction of labor. Any of the above-listed reasons (vaginal bleeding, spontaneous labor, premature rupture of membranes, etc) diagnosed at presentation will be reason to exclude the woman from participation. Furthermore, *after* Foley catheter placement, a patient may be excluded from the trial should any of the following occur:

1. She is diagnosed with a condition that requires immediate admission for induction of labor (such as gestational hypertension or preeclampsia)
2. She develops vaginal bleeding more than spotting that is clinically concerning for placental abruption
3. She spontaneously labors
4. She undergoes premature rupture of membranes
5. The post-placement fetal heart tracing is non reassuring such that outpatient management is not recommended
6. She develops a fever and/or chorioamnionitis

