#### **4.4.2 Data Collection and Follow-up for Withdrawn Subjects**

Data will not be collected from women who electively withdraw from the study. Data will be collected on all women who are randomized to a treatment group. Should patients from the outpatient group cross over to the inpatient group (i.e. if they meet exclusion criteria), analysis will be by intention to treat.

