## 7.4 Subject Population(s) for Analysis

We will analyze all subjects who were randomized in the randomized control trial design stage of the study, except those who electively withdrew from the trial. We will analyze all subjects enrolled in the prospective stage of the study, who do not electively withdraw.

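### With one analysis population for efficacy and safety, events that can happen only at home have no sent-home denominator, and the sections conflict on whether women kept in after placement are analysed

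*Combined protocol and SAP*

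**What the plan says.** Section 3.1, part IV, makes going home conditional: "The patient will be sent home if the following criteria are met", with conditions on the fetal tracing, membranes, labor, bleeding and maternal vital signs. So the plan itself foresees outpatient women who never leave the unit.

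Section 4.4.2 says of outpatient women that, should they "cross over to the inpatient group (i.e. if they meet exclusion criteria), analysis will be by intention to treat". It also says "Data will not be collected from women who electively withdraw from the study". Section 7.4 adds, for the current design: "We will analyze all subjects enrolled in the prospective stage of the study, who do not electively withdraw". No safety, as-treated or sent-home set is named.

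Other sections treat the same women differently. Section 1.4 says that after rupture of membranes, spontaneous labor or abruption during post-Foley monitoring, "she will be kept as an inpatient until delivery and excluded from the trial". For suspected abruption it says "the patient will be excluded from the trial and kept in the inpatient setting until delivery". Section 4.4.1 says that after placement "a patient may be excluded from the trial should any of the following occur", and lists six events.

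On outcomes, Section 3.4 makes severe pain a primary safety outcome and describes it as an overnight return to hospital. Section 3.3 (II) records expulsion at home and early return with its reason. Section 3.4 states that "we do not anticipate any difference between safety endpoints in the inpatient vs. outpatient groups".

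**The concern.** Section 1.1 says that the study should add evidence on safety for moving ripening to the outpatient setting. A reader will want to know how often something went wrong between dismissal and return. The plan collects those events, but the only population it defines includes women who were never at home.

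The conflict over exclusion is the other half of the problem. If women kept in are analysed, they lower the rate of at-home events. If they are excluded, the bleeding, ruptured membranes or abnormal tracings that followed placement drop out of the outpatient arm. Either way, a reported similarity between the groups would be hard to interpret.

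**Working it through.** **1. The plan's own figure.** Section 7.2 gives 40 and 160 women, a difference of 4 h, SD 8 h and two-sided 0.05. The standard error is 8 × √(1/40 + 1/160) = 1.414, and 4/1.414 = 2.83. Power is 80.7% by the normal approximation and 80.4% by the t distribution, so the stated 80% reproduces. It concerns hospitalization time only. The documents give no power, margin or event rate for safety.

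**2. Events possible only at home.** Let N be the outpatient women analysed, f the share not sent home and x the number of events. A woman kept in cannot contribute to x. The rate over all women is x/N; the rate over women sent home is x/[(1 - f)N]. Their ratio is exactly (1 - f), with no assumption about risk. As an illustration with N = 40 and x = 4, the rate is 10.0% over all 40, but 4/36 = 11.1% at f = 10% and 4/32 = 12.5% at f = 20%.

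**3. Precision with no events.** The exact two-sided 95% upper limit for 0/n is 1 - 0.025^(1/n):
- n = 40: 8.8%
- n = 36 (f = 10%): 9.7%
- n = 32 (f = 20%): 10.9%

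The range for f is an assumption.

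**4. All other safety endpoints.** The outpatient-arm risk is (1 - f) × p_home + f × p_stay, where p_stay is the risk in women kept in. Assume an inpatient risk of 5% and a sent-home risk of 15%, a true difference of 10 points. With 40 and 160 women, the difference and the power of Fisher's test are:

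| f | p_stay = 5% | p_stay = 15% | p_stay = 30% |
|---|---|---|---|
| 10% | 9.0 points, 46% | 10.0 points, 52% | 11.5 points, 61% |
| 20% | 8.0 points, 40% | 10.0 points, 52% | 13.0 points, 69% |

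The difference shrinks if women kept in have a lower risk than women sent home, is unchanged if the risks are equal, and grows if theirs is higher. All rates here are assumed.

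**5. Who is in the set.** Sections 4.4.2 and 7.4 keep women who meet exclusion criteria after placement. Section 1.4 removes those with ruptured membranes, labor or abruption, and Section 4.4.1 allows removal for these and for a non-reassuring tracing, fever or a new diagnosis. The two rules give different outpatient arms. Under the second, step 2's dilution disappears for the women removed, but so do their post-placement events.

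**The case against.** A reader might infer that intention to treat dilutes every safety risk and so pushes the result toward the expected finding of no difference. The documents do not support that. Women are kept in because of bleeding, labor, ruptured membranes, an abnormal tracing or fever. Several of these are safety endpoints in Sections 3.3 (IV) and 3.4, or close to them, so keeping these women in the outpatient arm may raise its event rate. Nor is it settled that safety is analysed only by intention to treat: Sections 1.4 and 4.4.1 point the other way, and the sentence in 4.4.2 stands beside text on randomized women, so its reach into the non-randomized stage rests on 7.4.

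The other objections also have weight:
- The objectives compare outpatient with inpatient groups. That is a question about a strategy, and intention to treat answers it. This stands, and is why the group comparison should not change.
- At-home events are already recorded. True; what is missing is their denominator.
- Small numbers are a larger cause of a finding of no difference. Also true: with no dilution at all, Fisher's test with 40 and 160 women has about 21% power for 5% against 10% and 52% for 5% against 15% (assumed rates).
- A sent-home set selects women who passed the discharge checks, with no matching selection in the controls. It cannot serve as the main comparison.

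What survives is a denominator for at-home events and a conflict over who is analysed.

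**Conclusion.** The point holds in a limited form. For events possible only at home, the single population lowers the rate by exactly (1 - f). This needs no assumption about risk, only that women kept in are analysed and that the 7.4 population is the denominator, since no other is named. At an assumed f of 10% to 20% the reduction is 10% to 20%, and the zero-event upper limit over women sent home is 9.7% to 10.9% rather than 8.8%.

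For the remaining safety endpoints no direction can be claimed. Nor can one say that the plan overstates its safety precision, because it states none. The conflict between Sections 1.4 and 4.4.1 on one side and 4.4.2 and 7.4 on the other is plain from the text and decides whether events in the monitored hour are counted. The remedy is a cheap improvement to safety reporting; the method for the primary comparison does not change.

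**What to change.** 1. Reconcile Sections 1.4 and 4.4.1 with 4.4.2 and 7.4. State that leaving the outpatient pathway is not removal from the analysis: every outpatient woman with a catheter placed is analysed in her assigned or enrolled group, except elective withdrawals. State also how women stopped at arrival, before placement, are counted.
2. Record for each outpatient woman whether she was sent home, and report f.
3. In Section 7.4 add a supplementary, descriptive safety table. One column gives events from dismissal to return over women sent home, with exact 95% confidence intervals. Beside it, give all safety endpoints for all women with a catheter placed, so that events in the monitored hour are kept. Base any statement on outpatient safety on both columns.
4. Keep intention to treat for the between-group comparison.

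The cost is the reconciling edits, one paragraph in 7.4, one recorded item and one table. Two drawbacks should be stated with the table: the sent-home denominator is smaller and its limits wider, and the set is selected by the discharge checks with no counterpart among the inpatient controls. It therefore supplements the group comparison and does not replace it.

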### **5 Study Drug**

#### **5.1 Description**

Please see section 1.2 for a description of the Foley catheter.

At Mayo clinic, the Foley bulb costs \$5.51 for the catheter and all necessary supplies. All resident level providers are trained in their first year to insert these catheters at Mayo clinic both in simulation models and in the Family Birth Center.

Please see section 1 for description of previous studies examining the Foley catheter as a means of cervical ripening in the outpatient setting.

#### **5.2 Treatment Regimen**

Please see sections 1.2 and 1.4.

#### **5.3 Method for Assigning Subjects to Treatment Groups in the Randomized Control Trial**

Through computer-generated randomization, women will be randomized on the morning of planned induction. They will be notified via telephone by the research coordinator. The randomization will be stratified by parity (primiparous vs. multiparous) and by body mass index ( $<30 \text{ kg/m}^2$  and  $\geq 30 \text{ kg/m}^2$ ).

#### **5.4 Preparation and Administration of Study Drug**

The following supplies should be gathered prior to insertion of the Foley catheter: one 16 French Foley catheter, one catheter plug, 60 cc of normal saline, one 60 cc syringe, sterile gel, and one pair of sterile gloves. The patient is appropriately for a pelvic exam. The examiner dons sterile gloves. He or she uses sterile gel and locates the cervical opening digitally. The tip of the Foley catheter is guided into cervix and through the internal os. The nurse then places the catheter plug in the outflow tract and injects 5 cc of normal saline into the inflow tract. The provider confirms that the balloon is in the appropriate position above the internal os. Then, the other 55 cc of normal saline are injected. The end of the catheter is taped to the patient's leg using foam tape.

Alternatively, depending on provider preference, the catheter can be placed using a speculum for guidance. In this case, the patient is placed in the lithotomy position. A speculum is inserted after the provider dons sterile gloves. Once the cervix is located, a ring forceps is placed on the anterior lip of the cervix. Another ring forceps is placed onto the tip of the catheter and is used to guide the catheter into the cervical os. Then, the balloon is inflated with 60 cc normal saline as above. Direct visualization confirms appropriate placement of the catheter. All other steps as described above are utilized.

#### **5.5 Subject Compliance Monitoring**

Not applicable.

## **5.6 Prior and Concomitant Therapy**

Information about concomitant pharmacologic pain control therapies will be collected. Please see the “protocol for the intervention group” in the section 3.1 above for a description of pain control options for the outpatient group. As this section states, non pharmacologic options (warm baths, massage, frequent position changes, relaxation techniques, gentle stretching), Tylenol, and Morphine 10 mg IM once before discharge are permitted for the intervention group. The inpatient group will have the standard array of pain control options that will be left to provider discretion.

## **5.7 Packaging**

The Foley catheter will be packaged by the manufacturer. A single device will be in a sterile, transparent wrapping.

## **5.8 Masking/Blinding of Study**

There is no blinding in this study. It is not logically possible to blind either the subjects or their providers.

## **5.9 Receiving, Storage, Dispensing and Return**

### **5.9.1 Storage**

The Foley catheters are already in use commonly on the Family Birth Center, and storage will not change. They are not removed from their package until minutes prior to their intended use. They may be exposed to light. They are stored in the Family Birth Center supply room, which is accessed only by a list of approved personnel using their identification badges.

### **5.9.2 Dispensing of Study Drug**

The Foley catheters are already in use commonly on the Family Birth Center, and dispensing will not change. The Foley catheters are stored in the Family Birth Center supply room. They will be obtained from this supply area individually for placement in each patient. If they are damaged inadvertently, they will not be utilized. If they are damaged during placement, the device will be discarded and a new catheter will be used.

## **6 Study Procedures**

### **6.1 Clinic visit**

Eligible patients will be identified, educated, and consented as described above in the Study Design section (3.1).

### **6.2 Initial arrival to the Family Birth Center (both groups)**

Please see the Study Design section under the headings “Protocol for the intervention (outpatient) group” and “Protocol for the inpatient (usual care) comparison/control group.”

Briefly, all patients will undergo the following upon arrival:

1. Non stress test
2. Ultrasound for fetal presentation
3. Ultrasound for amniotic fluid index

- (a) Not routinely completed in usual care of induction of labor.
- 4. Cervical exam
- 5. A set of standard questions as described in section 3.1
- 6. Maternal vital signs

### **6.3 Return to the Family Birth Center after dismissal home (intervention (outpatient) group only)**

When a patient in the intervention (outpatient) group is admitted to the hospital, either the next morning or any time in the middle of the night, she will undergo the following:

- 1. Non stress test
- 2. Ultrasound for fetal presentation
- 3. Cervical exam
- 4. Maternal vital signs

### **6.4 Inpatient postpartum stay**

Patients typically remain in the hospital between 24-72 hours after their delivery depending on mode of delivery and patient preference. During their inpatient stay, they will have their vitals checked per current protocol. Secondary endpoints will be collected during this time frame.

All subjects will be given the maternal satisfaction survey to complete prior to dismissal from the hospital. All efforts will be made by the research team to ensure the patient has completed the survey. If she does not complete the survey while in the hospital, she will be contacted by phone within the following 2 weeks by a member of the research team to complete it over the phone.

The maternal satisfaction survey has been adapted from the survey utilized by Henry et. al [11].

### **6.5 Postpartum follow up**

Secondary endpoints will be collected during the postpartum period. This is defined as 42 days after delivery or the final postpartum visit (typically at 6 weeks), whichever occurs later.

For patients who do not present to their postpartum visit, all available information in the electronic medical record will be used to determine the nature of the patient's postpartum course. A significant majority of low-risk obstetric patients live locally; therefore, we do not anticipate that adverse events will commonly be diagnosed and treated in other hospital systems.

## **7 Statistical Plan**

### **7.1 Sample Size Determination for Randomized Control Trial**

A power analysis was performed. With 64 patients per arm, we would have 80% power to detect a  $\frac{1}{2}$  standard deviation reduction in the hospitalization time for the outpatient group vs. the inpatient group, assuming a standard deviation of 8 (hours) and a reduction in the mean hospitalization time from 16 to 12 (hours) for the inpatient and outpatient groups, respectively. This also assumes a 2-sided significance level of 0.05.

This is a conservative estimate of the effect of the Foley catheter in the outpatient setting on pre-delivery hospitalization time, our primary outcome. The trial by Sciscione et al. [10]

observed that there was a reduction of 9.6 hours; Henry et al. found a reduction of 11.1 hours [11]. If we replicate this finding, we would be able to detect a difference in the primary outcome with a smaller number of patients, should we not meet desired enrollment.

## 7.2 Sample Size Determination for Prospective Study

A power analysis was performed and assumed a standard deviation of 8 hours. With 40 subjects in the Foley intervention arm and 160 subjects in the standard of care group, we would have 80% power to detect a  $\frac{1}{2}$  standard deviation reduction in the predelivery hospitalization time from 16 to 12 hours in the standard of care and intervention groups, respectively. This also assumes a 2-sided significance level of 0.05.

